Event-free survival will be estimated only for patients with leukemia presentation using the Kaplan-Meier method. EFS is defined as the time from first dose of study drug to treatment failure, relapse after CR (if applicable), or death from any cause, whichever occurs first. For a patient with none of these events before the end of study follow-up, observation of EFS is censored at the date of last contact prior to the analysis cut-off date. If the patient does not achieve a CR, EFS is defined as the point of treatment failure or death, whichever comes first. Treatment failure for EFS is defined as PD in this study.

Overall survival will be analyzed in a similar manner to PFS. In the absence of confirmation of death or for patients who are alive as of the OS cut-off date, survival time will be censored at the last known date that the patient was alive.

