- RFS will be evaluated only in patients with an objective response of CR. RFS will be estimated using the Kaplan–Meier method. RFS is measured from the first date of achieving CR until the first date of disease relapse or death from any cause, whichever occurs first. Patients who die without a reported disease relapse will be considered to have relapsed on the date of their death. Patients who did not relapse or die will be censored on the date of their last response assessment. Patients who started any subsequent anti-cancer therapy without a prior reported relapse will be censored at the last response assessment prior to initiation of the subsequent anti-cancer therapy. The censoring rule for RFS is in [Table 16](#).
- EFS will be estimated only in patients with leukemia presentation. EFS will be estimated using the Kaplan–Meier method. EFS is defined as the time from the first dose of study therapy to treatment failure, relapse after CR (if applicable), or death

from any cause, whichever occurs first. Treatment failure for EFS is defined as PD in this study. If the patient does not achieve a CR, EFS is defined as the point of treatment failure (PD) or death, whichever comes first. For a patient with none of these events before the end of the study follow-up, observation of EFS is censored at the date of the last contact prior to the analysis cut-off date. The censoring rule for EFS is described in [Table 17](#). Note that the start date of EFS is the same regardless of achieving a CR.

Table 15: Censoring Rules for Duration of CR and Duration of CR+CRi

No.	Situation	End Date	Outcome
1	Disease relapse between scheduled visits	Date of the first assessment that determined disease relapse	Event
2	Death during the study with no prior disease relapse	Date of death	Event
3	Patients still on treatment without disease relapse as of data cut-off ^a	Date of the last response assessment ^b	Censored
4	Treatment discontinuation for reasons other than disease relapse or death	Date of the last response assessment	Censored
5	New anticancer treatment started	Date of the last response assessment before start of new treatment	Censored
6	Death or disease relapse after two or more missed response assessments ^c	Date of the last response assessment before missed assessments	Censored

^aThis refers to patients who were still receiving study treatment at time of data cutoff.

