^bFor duration of CR and duration of CR+CRi, the date of last response assessment refers to the date of last adequate response assessment.

^cTwo or more missed response assessments is defined as having either one of the following two durations being longer than 126 days (= (28 [days/cycle] x 2 [cycles] + 7 [days]) x 2):

Duration between two consecutive response assessments

Duration between the last response assessment and death or disease relapse

Table 16: Censoring Rules for Relapse-free Survival (RFS)

No.	Situation	Event or Censoring Date	Outcome
1	Disease relapse between scheduled visits	Date of the first assessment that determined disease relapse	Event
2	Death during the study with no prior disease relapse	Date of death	Event
3	Patients still on treatment without disease relapse as of data cut-off ^a	Date of the last response assessment ^b	Censored
4	Treatment discontinuation for reasons other than disease relapse or death	Date of the last response assessment	Censored
5	New anticancer treatment started	Date of the last response assessment before start of new treatment	Censored
6	Death or disease relapse after two or more missed response assessments ^c	Date of the last response assessment before start of new treatment	Censored

^a This refers to patients who were still receiving study treatment at time of data cutoff.

^b For RFS, the date of last response assessment refers to the date of last adequate response assessment.

^cTwo or more missed response assessments is defined as having either one of the following two durations being longer than 126 days (= (28 [days/cycle] x 2 [cycles] + 7 [days]) x 2):

Duration between two consecutive response assessments

Duration between the last response assessment and death or disease relapse

Table 17: Censoring Rules for Event-Free Survival (EFS)

No.	Situation	Event or Censoring Date	Outcome
If a patient achieved a CR at the analysis, the following rules (No. 1 to 6) will be applied.			
1	Disease relapse between scheduled visits	Date of the first assessment that determined disease relapse	Event
2	Death during the study with no prior disease relapse	Date of death	Event
3	Patients still on treatment without disease relapse as of data cut-off ^a	Date of the last response assessment ^b	Censored
4	Treatment discontinuation for reasons other than disease relapse or death	Date of the last response assessment	Censored

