5	New anticancer treatment started	Date of the last response assessment before start of new treatment	Censored

No.	Situation	Event or Censoring Date	Outcome
6	Death or disease relapse after two or more missed response assessments ^c	Date of the last response assessment before start of new treatment	Censored
If a patient did not achieve a CR at the analysis, the following rules (No. 7 to 11) will be applied.			
7	Documented PD between scheduled visits	Date of the first assessment that determined PD	Event
8	Death during the study with no prior PD	Date of death	Event
9	Patients still on treatment without PD as of data cut-off ^a	Date of the last contact	Censored
10	Treatment discontinuation for reasons other than PD or death, and no post baseline response assessments	Date of the first dose	Censored
11	Treatment discontinuation for reasons other than PD or death with post baseline response assessments	Date of the last contact	Censored
12	New anticancer treatment started	Date of the last contact	Censored
13	Death or PD after two or more missed response assessments ^c	Date of the last contact	Censored
14	No baseline or unreadable baseline assessment but readable post baseline assessments	Date of the first dose	Censored

^a This refers to patients who were still receiving study treatment at time of data cutoff.

^b For EFS, the date of last response assessment refers to the date of last adequate response assessment.

^c Two or more missed response assessments is defined as having either one of the following two durations being longer than 126 days (= (28 [days/cycle] x 2 [cycles] + 7 [days]) x 2):

Duration between two consecutive response assessments

Duration between the last response assessment and death or disease relapse

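### SAP Table 17 contradicts the EFS rule in protocol 11.5.3.2.2 and in the SAP's own text, and states no precedence among its rows

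*SAP*

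**What the plan says.** Protocol 11.5.3.2.2 states the endpoint, which applies to the leukemia subset only: "EFS is defined as the time from first dose of study drug to treatment failure, relapse after CR (if applicable), or death from any cause". PD is what counts as failure of treatment. When no such event has occurred, "observation of EFS is censored at the date of last contact prior to the analysis cut-off date". The synopsis and the Amendment 1 text say the same.

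The SAP paragraph on EFS in 5.5.2.2 agrees: "observation of EFS is censored at the date of the last contact prior to the analysis cut-off date". Neither text varies the rule by CR status, and neither names new therapy or missed assessments as a reason to censor. The protocol does write new-therapy censoring for PFS, the duration endpoints and RFS in the same section, but not for EFS.

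The SAP paragraph then points to Table 17, which divides patients into two blocks. The first opens "If a patient achieved a CR at the analysis, the following rules (No. 1 to 6) will be applied". The second opens "If a patient did not achieve a CR at the analysis, the following rules (No. 7 to 11) will be applied", but its rows go on to 14. SAP section 6 declares no change to the planned analyses.

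**The concern.** The text and the table cannot both be followed. The table censors patients whom the definition counts as having events, and for CR patients it uses a different censoring date from the one in the text. Because several rows can fit one patient and no order is given, two programmers working correctly from the SAP could produce different EFS curves. The leukemia-presentation subset will be small, so the status of a single patient can move the estimate visibly.

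**Working it through.** **Inputs.** Event definition and last-contact rule: protocol 11.5.3.2.2 and SAP 5.5.2.2. Row contents and the gap definition: SAP Table 17 and its footnote c. Response assessments stop at new therapy: protocol 3.3.4. Survival contact continues every 12 weeks: protocol 3.3.5. Cohort C has about 20 patients: protocol 11.1. The number with leukemia presentation is not given.

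**The plan's own figure.** Footnote c sets the gap at (28 × 2 + 7) × 2 = 63 × 2 = 126 days, which reproduces.

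**Text and table side by side.**

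| Situation | Protocol and SAP text | Table 17, CR | Table 17, no CR |
|---|---|---|---|
| On treatment at cut-off, no event | last contact | last response assessment (row 3) | last contact (row 9) |
| Off treatment, assessed, no event | last contact | last response assessment (row 4) | last contact (row 11) |
| Off treatment, never assessed after baseline, no event | last contact | no row | first dose (row 10) |
| No usable baseline assessment | event, else last contact | no row | first dose (row 14) |
| New therapy, no later event | last contact | last assessment before it (row 5) | last contact (row 12) |
| New therapy, then death | event | event (row 2) or censored (row 5) | event (row 8) or censored (row 12) |
| Death, relapse or PD after a gap over 126 days | event | censored (row 6) | censored (row 13) |

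The contrast between rows 4 and 11 is between "Treatment discontinuation for reasons other than disease relapse or death" and "Treatment discontinuation for reasons other than PD or death with post baseline response assessments": the same situation with two date rules. Row 6 takes its date from "Date of the last response assessment before start of new treatment", although the row concerns missed assessments and the patient may never have had a new treatment. The matching row of Table 15 uses the last assessment before the missed ones.

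**Identical dates run through both rules** (days from first dose; example dates, not from the documents).

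1. On treatment at cut-off, last assessment 168, last contact 197. Text: censored at 197. Table: 168 with CR, 197 without. Difference 197 − 168 = 29 days.
2. Off treatment without an event, last assessment 168, last contact 252. Text: censored at 252. Table: 168 with CR, 252 without. Difference 252 − 168 = 84 days.
3. Last assessment 168, new therapy 180, last contact 240, death 250. The gap is 250 − 168 = 82 days, under 126, so rows 6 and 13 do not apply. Text: event at 250. Table with CR: event at 250 (row 2) or censored at 168 (row 5). Table without CR: event at 250 (row 8) or censored at 240 (row 12). Under the literal header, row 12 is not assigned to anyone, which leaves row 8.
4. No new therapy, last assessment 168, last contact 290, death 300. The gap is 300 − 168 = 132 days, over 126. Text: event at 300. Table without CR: row 13 censors at 290. Table with CR: row 6 censors, at a date the row does not properly define. These rows name death and mark it censored, although rows 2 and 8 still call it an event.

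**Illustrative size.** A large simulation used assumptions that are not in the documents: CR 50%; median time to PD or relapse 365 days with CR and 150 without; 10% to 40% of patients assigned to new therapy without PD at day 28 to 300; median survival after it 120 to 365 days; cut-off 183 to 730 days after first dose. Rows 6 and 13 were not modelled.

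- If rows 5 and 12 override rows 2 and 8, about 4% to 27% of protocol events become censored. Twelve-month EFS changes by between −0.7 points (37.7% to 37.0%) and +8.5 points (30.7% to 39.2%).
- If row 12 is left out, as the header literally says, the change runs from −3.0 points (40.1% to 37.1%) to +1.6 points (30.7% to 32.3%).
- The choice between these two readings alone is worth up to 39.2 − 32.3 = 6.9 points.

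**The case against.** The strongest defence is that the stakes are low and that part of the table follows house convention. EFS is one of several Cohort C secondary endpoints, has no hypothesis test, and covers a subset of about 20 patients. Every death up to cut-off still counts in overall survival. Censoring at new therapy is this study's rule for PFS, the duration endpoints and RFS. Patients enter Cohort C as not candidates for other therapies (protocol 4.1), so new therapy before PD may be uncommon. All of this stands and limits the importance of the point. It does not reconcile the table with the paragraph that introduces it.

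A reader might also infer more than the documents support:

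- *That censoring depends on a future outcome.* SAP 5.5.2.1 excludes responses recorded after progression or new therapy, and a CR cannot postdate the last response assessment. At each censoring date in the CR block, the CR has already happened. The two date rules are inconsistent, but they do not look ahead.
- *That row 12 wrongly credits time on the next treatment.* For a living patient without an event, last contact is the protocol's own censoring date. Row 12 departs from it only when an event follows.
- *That deaths after new therapy are certainly censored.* That needs rows 5 and 12 to override rows 2 and 8, and no precedence is written. Only rows 6 and 13 name deaths as censored.

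**Conclusion.** Table 17 is wrong as written. It contradicts the protocol and the SAP text on censoring dates (rows 3, 4, 10 and 14), adds new-therapy censoring that the EFS text lacks (rows 5 and 12), censors deaths, PD and relapse after a gap (rows 6 and 13), and has a header that stops at row 11. The EFS rule is the same in Amendment 1 and Amendment 2, so the mismatch does not come from the SAP preceding an amendment.

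The real size cannot be computed, because the documents give neither the number of leukemia-presentation patients nor the rate of new therapy or missed assessments. If there were 5 to 10 such patients (an assumed 25% to 50% of 20), one reclassified death with all of them still at risk would be a step of 1/10 to 1/5, or 10 to 20 points. How often that would occur is unknown. A reader might conclude that EFS would be uninterpretable; that is not shown. The primary CR rate, sample size and type I error are unaffected. The table should be corrected before the Cohort C analysis.

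**What to change.** Replace Table 17 with one set of rows for all leukemia-presentation patients, matching protocol 11.5.3.2.2 and the SAP text. PD, relapse after CR or death from any cause is an event on its date, including after new therapy or missed assessments. A patient with no event is censored at last contact before cut-off. Drop the split by CR status and the first-dose rows.

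If the sponsor wants censoring at new therapy or after missed assessments, present it as a declared sensitivity analysis with one date rule for everyone and a stated row precedence.

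The cost is one SAP table. Deaths and subsequent therapies are already collected under protocol 3.3.5, so no new data are needed. EFS may come out shorter than under the current table.

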		D1 (±3 days)	D8 (±3 days)	D15 (±3 days)	D22 (±3 days)	D1 (±3 days)	End of Cycle (±7 days)		
PET scan	X				See Note				PET scan to be performed at baseline visit, end of Cycle 1 (± 7 days) if baseline is abnormal, and as clinically indicated for response assessment.
Lymph node biopsy	X	See Note							Recommended at baseline visit if lymph node present at baseline and progression
Bone marrow tissue submission	X	See Note							Archival or fresh bone marrow biopsy tissue sample needs to be submitted at baseline visit. In addition, bone marrow biopsy should be performed in case of normalization of peripheral blood count during the futibatinib treatment. In absence of peripheral blood count normalization, biopsy to be performed every 6 months. Additional biopsies to be performed as clinically indicated.
Survival status								X	For all patients, unless patient withdraws consent or the study is terminated early by the Sponsor.

Table 3: Schedule of Events – Study Extension Phase: All Cohorts

	Treatment Period At Least Every 3 Cycles	Safety Follow-up 30 (+7) Days After last Dose	Notes
Physical examination	X	X	Within 24 hours prior to dosing on D1
Vital signs	X	X	Heart rate, blood pressure, body temperature, and respiration rate.
Weight	X	X	
Ophthalmological examination	(X)	X	As needed due to local requirements, physician judgment, and/or symptoms or signs of mineral deposits.
12-Lead electrocardiogram	X	X	
Hematology and coagulation	X	X	Within 24 hours prior to dosing on D1
Chemistry (serum or plasma)	X	X	Within 24 hours prior to dosing on D1
Pregnancy test	X		More frequently if required by local regulations.
Prior & concomitant medications, AE assessments	(X)	X	Collect from the time main informed consent is signed through 30 days after administration of the last dose of study drug or until the start of new anticancer therapy, whichever is earlier.
Response assessments/imaging	(X)		All Cohorts: CT/MRI scans at baseline and the end of every 2 cycles (± 7 days), or as clinically indicated, until radiologic PD or initiation of new anticancer therapy (whichever comes first). Cohort C only: bone marrow, PET, and other response assessments as clinically indicated.

TABLE OF CONTENTS

SUMMARY OF CHANGES.....	2
STUDY SUMMARY	6
Protocol Synopsis	6
Study Schema.....	17
Schedule of Events.....	18
LIST OF ABBREVIATIONS AND DEFINITIONS OF TERMS.....	31
1. INTRODUCTION	35
1.1. Disease Background	35
1.2. Futibatinib (TAS-120)	36
1.2.1. Clinical Overview	36

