8.2. Cohort C

8.2.1. Efficacy Criteria

Efficacy will be assessed by evaluation of:

- Bone marrow histomorphology changes, standard cytogenetics, and *FGFR* molecular status
- Peripheral blood assessment (blood count) including potentially *FGFR* molecular status
- Positron emission tomography (PET) scan for fluorodeoxyglucose (FDG) avid lesions
- Imaging (CT/MRI) in case of presence of solid lesions
- Clinical assessment

If the Investigator determines that a patient has developed clinical disease progression manifested by symptomatic deterioration, the patient may stop treatment. Every effort should be made to document objective disease progression even after discontinuation of treatment.

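### The SAP's 126-day missed-assessment limit fits Cohort C patients followed by 8-weekly CT/MRI, but in marrow-judged disease it can censor relapse, progression or death when no visit was missed

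*SAP*

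**What the plan says.** In SAP 5.5.2.2, row 6 of Table 15 (duration of CR and of CR+CRi) censors this situation: "Death or disease relapse after two or more missed response assessments". Table 16 (RFS) and Table 17 (EFS) carry the same row, and Table 17 adds row 13 for patients who did not reach CR. Cohort C PFS and DOR are sent to Tables 10 and 12, which hold the equivalent row for tumor assessments. OS is the only Cohort C time-to-event endpoint outside the rule.

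The footnote reads "Two or more missed response assessments is defined as having either one of the following two durations being longer than 126 days" and derives the figure from two 28-day cycles plus a 7-day window, doubled. The two durations are:

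- "Duration between two consecutive response assessments"
- "Duration between the last response assessment and death or disease relapse"

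On what counts as an assessment, the SAP says only that "the date of last response assessment refers to the date of last adequate response assessment". It names no modality.

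The protocol gives Cohort C several schedules. Table 2 has CT/MRI at the end of every 2 cycles (±7 days) and hematology on Day 1 of every cycle. For marrow it asks for a biopsy when blood counts normalize on treatment, and otherwise: "In absence of peripheral blood count normalization, biopsy to be performed every 6 months". Further biopsies are left to clinical indication. Protocol 8.2.1 lists marrow, blood counts, PET and clinical assessment as efficacy evaluations, and adds "Imaging (CT/MRI) in case of presence of solid lesions".

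**The concern.** The number was built for an 8-week imaging schedule and carried into tables whose wording had been changed from tumor to response assessments. Where response is read from marrow and there is no solid lesion to image, the relevant visit may be 6 months after the last one by design. The rule would then treat a fully compliant patient as having missed visits and remove a real event.

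Protocol 11.5.3.2.2 has no such rule. It counts relapse, progression and death as events, and it censors only patients without an event or those who started new anticancer therapy. SAP Section 6 nevertheless reports no changes to the planned analyses.

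The endpoints at risk are PFS, DOR, duration of CR, duration of CR+CRi, RFS and EFS. The cohort has about 20 patients. At the target CR rate of 50% that is 20 × 0.50 = 10 complete responders, so a few events turned into censorings could move a Kaplan–Meier median or leave it unestimated. The study is open-label, so an undefined term could also end up being settled with the data in view.

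**Working it through.** **Inputs.** 28-day cycles, imaging every 2 cycles with ±7 days, and Day 1 visits with ±3 days (Protocol Table 2); the 126-day limit and its two gaps (SAP Table 15, footnote c). The documents give no day count or window for the 6-month marrow. I assume 168 days (6 × 28) to 184 days (six calendar months).

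**1. The plan's figure.** (28 × 2 + 7) × 2 = 126 days. It reproduces exactly.

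**2. Does it work for 8-week imaging?**

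- No scan missed, longest gap: 56 + 7 + 7 = 70 days.
- One scan missed, longest gap: 112 + 7 + 7 = 126 days.
- Two scans missed, shortest gap: 168 − 7 − 7 = 154 days.

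A gap longer than 126 days therefore separates two missed scans from one. For CT-followed patients the limit is sound.

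**3. If an adequate assessment requires marrow.** One on-time interval exceeds the limit by 168 − 126 = 42 days to 184 − 126 = 58 days.

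- An event first found at the on-time 6-month biopsy always falls beyond 126 days and is censored.
- For a death within the first interval, only the gap from last assessment to event matters. If deaths fall uniformly over the interval, the censored share is 42/168 = 25% to 58/184 = 32%.
- The other gap is not limited to the one just before the event. Once one full on-time interval has passed, the record contains a gap over 126 days, and as written any later event meets the rule. The 25% to 32% therefore applies to the first interval only.

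**4. If 8-weekly CT/MRI or Day 1 blood counts qualify.** The longest on-schedule gaps are 70 days (step 2) and 28 + 3 + 3 = 34 days. Both are below 126, so no on-schedule event is censored.

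**5. Which patients.** The 6-month interval applies while counts have not normalized. That can include CRi (by name, incomplete hematological recovery), PR and non-responding patients, and so touches DOR, duration of CR+CRi, PFS and EFS row 13. Once counts normalize there is no fixed marrow interval. A marrow visit cannot then be missed, and no day limit follows from the schedule.

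**6. Where the censored time goes.** Table 15 row 6 uses the last assessment before the missed ones. Table 17 row 13 uses the date of last contact, so there the event is lost but the time is not moved back to an earlier assessment.

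**7. The SAP's formula applied to marrow.** (168 + 7) × 2 = 350 to (184 + 7) × 2 = 382 days, borrowing the imaging window; without a window, 336 to 368 days.

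**The case against.** The strongest reply is that 126 days matches one of Cohort C's own schedules. Protocol Table 2 puts CT/MRI every 8 weeks with no solid-lesion condition in that row. Protocol 3.3.4 describes 8-weekly response assessments after discontinuation, and Table 3 lists CT/MRI for all cohorts in the extension. Response draws on imaging, blood and extramedullary disease as well as marrow (Protocol 8.2.3). On that reading step 4 applies and nothing on schedule is lost. This stands as far as it goes, but the SAP does not adopt it. Protocol 8.2.1 makes imaging an efficacy modality conditional on solid lesions, and SAP 5.5.2.1 itself requires at least two marrow assessments to confirm CR when the first shows fibrosis.

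A reader might go further and infer that relapses in CR patients found at a scheduled 6-month marrow are always censored, leaving the median duration of CR not reached. The documents do not support that. The 6-month interval is conditional on counts not having normalized, which is not the expected state of a patient in CR, and the SAP does not say that marrow is required. Nor do they support calling the limit wrong for the whole cohort: it is sound for patients followed by CT, such as a lymphoma presentation with measurable nodes.

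**Conclusion.** The limit is correct for 8-weekly CT/MRI and has no basis in the schedule for marrow-assessed disease without solid lesions. Whether it does harm depends on a term that the SAP leaves undefined. On-schedule loss ranges from nil, if CT or Day 1 counts qualify, to every event first detected at an on-time 6-month biopsy, if marrow is required. On the marrow reading, the either-gap wording extends the loss to later events.

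This rests on 6 months being 168 to 184 days, on uniform timing for the death share, and on MLN-only and leukemia presentations being those judged mainly on marrow, since the documents do not map modality to presentation explicitly. It concerns secondary endpoints in about 20 patients and does not touch the primary CR rate. It should still be changed, because a stated numerical rule gives a wrong answer under a natural reading and departs from the protocol's event definitions.

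**What to change.** In the SAP:

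- For the main Cohort C analyses of marrow-assessed presentations (MLN only, leukemia), count documented relapse, progression and death on their dates. This means dropping the missed-assessment rows from Tables 15 to 17, and from Tables 10 and 12 as used for these patients.
- Keep missed-assessment censoring only as a sensitivity analysis. State by presentation which assessment qualifies as adequate, and tie the gap to that assessment's schedule: 126 days for CT-followed disease such as lymphoma presentation, and a marrow-based gap, with its window defined, where a fixed marrow interval exists.
- Apply the gap only to the interval immediately before the event.

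The cost is SAP wording, with no new data or visits. The downside is that reported durations may be shorter, because events now censored would count.
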